9.2 Statistical analyses

9.2.1 General considerations

Data analyses are described in Section 9 of the study protocol with more details available in statistical analysis plan (SAP).

Unless specified otherwise, baseline is defined as the measurement obtained at the end of runin (Visit 30) or randomization visit (Visit 100) whichever occurs last, or the measurement obtained at an earlier visit (scheduled or unscheduled) which was closest to the Visit 30/Visit 100, if Visit 30/Visit 100 measurement is missing.

All efficacy analyses will be based on FAS and all safety analyses will be based on SAF unless specified otherwise. In descriptive summaries, continuous variables will be summarized using n, mean, standard deviation (SD), median, minimum, 25th percentile (Q1), 75th percentile (Q3), and maximum; categorical variables will be summarized using frequency and percentage.

9.2.2 Participant demographics and other baseline characteristics

Demographic and other baseline data including disease history and standard background medications will be summarized descriptively by treatment group for the FAS and RAS.

Relevant medical histories and current medical conditions at baseline will be summarized by system organ class and preferred term, by treatment group and overall.

9.2.3 Treatments

The duration of exposure in day(s) will be summarized by means of descriptive statistics and treatment group using the safety set. Concomitant medications and significant non-drug therapies prior to and after the start of the study treatment will be summarized by treatment group.

Number and percentage of participants on different antihypertensive medications as well as the doses will be summarized by treatment at baseline, Week 4, Week 8 and Week 12 during the randomized treatment period, and at Week 16 and Week 20 during safety follow-up period. The FAS and SAF will be used for these analyses.

9.3 Primary endpoint(s)/estimand(s) analysis

Primary estimands are described in Section 3.1. The primary endpoint and statistical analysis will be described in this Section.

9.3.1 Definition of primary endpoint(s)

The primary efficacy variable is change from baseline in mean 24 hr SBP at Week 12.

Missing values at Week 12 will be imputed as described in Section 9.3.3 and Section 9.3.4.

9.3.2 Statistical model, hypothesis, and method of analysis

The primary objective of determination of a dose-response signal and to characterize the dose-response relationship in XXB750 doses compared to placebo will be evaluated using an optimally weighted contrast test following the Multiple Comparison Procedure-Modeling (MCP-MOD) methodology described in (Pinheiro et al 2006, Pinheiro et al 2014).

A candidate model set is defined corresponding to the range of the expected mean response in each of the dose groups. The candidate model set is used to generate a set of weights for the calculation of optimal contrasts between the responses in the studied dose groups and the placebo group. A statistical test comparing all doses in the different dose groups simultaneously to the placebo is used, hence a multiplicity adjustment is applied that accounts for the multiple possible dose response behavior considered. A critical value is derived from a multivariate t-distribution using the correlation matrix induced by the correlations between the weights corresponding to the candidate sets as well as the correlation between the tests of shapes in the dosing groups to the placebo group.

Test of the dose response signal

The null hypothesis of a flat dose-response relationship for the change from baseline in mean 24-hour ambulatory systolic blood pressure (mean 24 hr SBP) compared to placebo will be tested at a 1-sided significance level of 2.5% against the alternative hypothesis of a dose-response relationship leading to a significant reduction in the mean 24 hr SBP.

Hence, the following null and alternative hypotheses will be tested:

[figure not shown]
- **H**₁₀: there is no dose-response relationship for XXB750 (i.e. all dose groups have the same response mean as the placebo group).
- **H**₁₁: there is a dose-response relationship for XXB750 (i.e. at least one dose-groups has a response mean different from the placebo group).

There are five candidate models to capture the shape of the dose-response relationship for XXB750 at Week 12 endpoint, as depicted in Figure 9-1. The candidate models generating the contrast weights are described below:

Model 1: Emax with ED50 at 30 mg SC q4w

- Model 2: Emax with ED50 at 60 mg SC q4w
- Model 3: sigmoid Emax with ED50 at 30 mg SC q4w and hill parameter h=3
- Model 4: sigmoid Emax with ED50 at 120 mg SC q4w and hill parameter h=3
- Model 5: Beta-model with delta1=0.2, delta2=0.3 and scale=288

Figure 9-1 Dose-response curve of candidate models

The analysis to derive the test statistics is based on an analysis of covariance (ANCOVA) model with the change from baseline mean 24 hr SBP at Week 12 as response variable, treatment (placebo and XXB750 dose groups), number of antihypertensive medications (3 or >3), and region as factors, and the baseline mean 24 hr SBP as a covariate.

The response variable of the change in mean 24 hr SBP from baseline at Week 12 used in the above ANCOVA model is from an imputed dataset, where missing Week 12 mean 24 hr SBP using the multiple imputation method described is imputed as in Section 9.3.3 and Section 9.3.4. In order to account for the imputation uncertainty, this ANCOVA model will be repeated for each imputed dataset, which results in a set of least squares (LS) mean estimate for all treatment groups and the related covariance matrices. Rubin's rule will be used to combine the multiple sets of LS mean estimates and the related covariance matrices to a single set of LS mean estimates of change of mean 24 hr SBP at Week 12 for all treatment groups and the related covariance matrix.

The optimal contrasts derived from the candidate model sets will be applied to the combined estimated dose means and covariance matrix to obtain t statistics for each candidate model and the common critical value $C_{0.025}$. $C_{0.025}$ is the common critical value derived from the reference multivariate t-distribution with the 5x5 correlation matrix induced by test the candidate dose response models with respect to comparing all XXB750 dose groups to placebo.

The H_{10} will be rejected and the statistical significance of dose-response in mean 24hr SBP reduction is established if the max(t1, t2,..., t5) $\geq C_{0.025}$.

Model averaging to obtain the dose response

A parametric bootstrap-based model averaging approach (Pinheiro et al 2014) will be implemented to obtain the dose response estimates according to the following steps:

- 1. The parametric bootstrap procedure will draw a sample of changes of mean 24 hr SBP from baseline to Week 12 for all doses (including placebo) from a multivariate normal distribution, with mean and covariance matrix was determined using Rubin's rule, as described earlier. This sample corresponds to the mean response for each dose (including placebo).
- 2. Model selection will be performed as follows: general dose-response models as specified will be fit to this bootstrap sample, i.e. Emax, Sigmoid Emax and β -model will be fit to mean response data from placebo and XXB750 doses. The best model based on the gAIC criterion will be selected.
- 3. The dose response estimate will be calculated for each dose group, including placebo, using this selected model. The difference in estimated dose response between each dose and placebo will also be calculated.
- 4. The above procedure (steps 1-3) will be repeated 5,000 times. The mean dose-response estimates by dose group and mean differences of dose-response estimates between each XXB750 dose and placebo, the target doses of interest, as well as their 95% confidence intervals will be calculated based on the quantiles (median, 2.5th and 97.5th percentiles) of these multiple sets of dose-response and target dose estimates generated in step 3. In addition, the bootstrapping model-based medians over the range from 0 mg (placebo) to 240 mg with 95% point-wise confidence interval (2.5th and 97.5th percentiles) will be displayed in a figure.

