4.1 Overall design

Study XXB750B12201 is a multicenter, randomized, double-blind, placebo-controlled, parallel-group phase 2 study which is comprised of four periods (Figure 1-1):

- A screening period (approximately 7 days)
- A single-blind placebo run-in period lasting approximately 2 weeks
- A 12-week double-blind, placebo-controlled, parallel-group treatment period
- An 8-week safety follow-up period

The study will enroll participants with rHTN defined as patients with uncontrolled BP despite treatment with optimal or maximally tolerated doses of 3 or 4 antihypertensive drugs of different classes, specifically a thiazide/thiazide-like diuretic, an ACEI or an ARB, and a long acting dihydropyridine CCB. Approximately 170 participants will be randomized to receive placebo, XXB750 30 mg, 60 mg, 120 mg, or 240 mg SC every 4 weeks, at an overall final ratio of 1:1:1:1:1. The overall design of the study is depicted in Figure 1-1.

A staggered approach to enrollment will be followed in this protocol. As summarized in Table 4-1, the randomized participant sample will be divided into two groups, which will vary in terms of the ratio of allocation to the treatment arms. Group 1 will consist of approximately 68 participants who will be randomized to either placebo, XXB750 30 mg SC every 4 weeks (dose level 1), XXB750 60 mg SC every 4 weeks (dose level 2), or XXB750 120 mg SC every 4 weeks (dose level 3) in a 1:1:1:1 ratio. The Data Monitoring Committee (DMC) will review the safety data of the Group 1 participants when approximately 40 participants have completed at least the first 5 weeks of randomized treatment. If the safety profile of XXB750 dose levels 1, 2 and 3 is deemed acceptable by the DMC, Group 2 enrolment will start upon full completion of Group 1 enrollment. Group 2 will consist of approximately 102 participants who will be randomized to either placebo, XXB750 dose level 1, XXB750 dose level 2, XXB750 dose level 3, or XXB750 120 mg SC for one injection followed by 240 mg SC every 4 weeks for two injections beginning 4 weeks after the first dose (dose level 4) in a 1:1:1:1:2 ratio. All participants will be followed for 8 additional weeks after end of dosing of the study medications to monitor their safety.

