In the event that the DMC recommends that participants should not be exposed to XXB750 240 mg dose, the study will continue without it, and dose level 4 will be eliminated from the study. In this case, the Group 2 enrollment will consist of approximately 68 participants randomized to either placebo, XXB750 dose level 1, XXB750 dose level 2, or XXB750 dose level 3 in a 1:1:1:1 ratio.

Table 4-1 Overview of staggered enrollment strategy

Treatment arm	Group 1	Group 2	Total	
		(adjusted*)	(adjusted*)	
Placebo	n = 17	n = 17	N = 34	
XXB750 30mg SC every 4 weeks	n = 17	n = 17	N = 34	

Treatment arm	Group 1	Group 2 (adjusted*)	Total (adjusted*)
XXB750 60mg SC every 4 weeks	n = 17	n = 17	N = 34
XXB750 120mg SC every 4 weeks	n = 17	n = 17	N = 34
XXB750 120mg SC x 1 dose, then XXB750 240mg every 4 weeks	n = 0	n = 34 (0*)	N = 34 (0*)
Total	N = 68	N = 102 (68*)	N = 170 (136*)

^{*} Adjusted numbers are applicable if DMC recommends against administration of dose level 4 in the Group 2 enrollment.

Refer to Section 1.2 Schema for study design figure.

The following is an overview of the study procedure plan. All office visits should be conducted at approximately the same time throughout the study, which should be approximately between 07:00am and 11:00am. The participant should be instructed not to take any of the background antihypertensive therapy medications prior to the scheduled office visit, but bring their antihypertensive medications to the study site so they can take them after all of the office study assessments are complete witnessed by the investigator or designee. At clinic visits when re ABPM assessment is scheduled, patients should not take their triple background antihypertensive medications until after all office assessments are complete and immediately before attaching the ABPM device.

Screening

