4.6 Purpose and timing of interim analyses/design adaptations

A staggered approach is planned to generate safety data in the target rHTN population with the three lower doses of XXB750 before enrolling participants to receive the highest dose. The staggered enrollment will follow the strategy outlined in Section 4.1 Table 4-1. In this strategy, 17 participants will be exposed to each of the lower doses of XXB750 (dose level 1, dose level 2 and dose level 3), and 17 participants will be exposed to placebo. The DMC will conduct an interim safety analysis on data of approximately 40 participants who complete at least 5 weeks of double-blind treatment. If the safety profile of the 3 lower XXB750 doses is acceptable, approximately 102 additional participants will be randomized and exposed to study medications (17 on XXB750 dose levels 1, 2, 3 and placebo and 34 participants on XXB750 dose level 4).

In addition to the planned early interim safety analysis, there will be safety data reviews conducted regularly by the DMC. Refer to Section 10.1.4 for more information about the role of the DMC in this study.

The primary analysis will be performed after all participants have completed Week 12 (or discontinued prior to Week 12). A final analysis will be performed after all participants have completed Week 20 (or discontinued prior to Week 20). Please see Section 9.8 for more details.

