9.3.5 Multiplicity adjustment (if applicable)

Please refer to Section 9.3.2 for primary analysis of MCP-MOD for multiplicity adjustment with respect to testing for a dose response signal across multiple candidate shapes. The secondary hypotheses included in the order of hierarchical testing procedure are: (1) evaluate and demonstrate treatment effect of highest XXB750 dose group versus placebo in reducing the mean 24hr SBP from baseline to Week 12, (2), evaluate and demonstrate treatment effect of highest XXB750 dose group versus placebo in reducing the average of mean 24hr SBP from baseline to Week 9 and Week 12 and (3) dose-response relationship in terms of proportions of participants achieving BP control among XXB750 dose groups and placebo. The secondary hypotheses will be tested in the order described above and statistical inference will be made only if the primary hypothesis is rejected.

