There are five candidate models to capture the shape of the dose-response relationship for XXB750 with respect to the proportion of participants with BP control at Week 12, as depicted in Figure 9-2. The candidate models generating the contrast weights are described below:

- Model 1: Emax with ED50 at 30 mg SC q4w
- Model 2: Emax with ED50 at 60 mg SC q4w
- Model 3: sigmoid Emax with ED50 at 30 mg SC q4w and hill parameter h=3
- Model 4: sigmoid Emax with ED50 at 120 mg SC q4w and hill parameter h=3
- Model 5: Beta-model with delta1=0.2, delta2=0.3 and scale=288

Figure 9-2 Dose-response curve of candidate models for proportion of participants with BP control

The analysis method of generalized MCP-Mod for binary data is similar as the primary analysis described in Section 9.3.2, but with the response for participant i in treatment k, Y_{ki} , follows a Bernoulli(p_k), where p_k is the probability of participants achieving BP control in treatment group k. And logit(p_k) will be estimated using a logistic regression with treatment (placebo and XXB750 dose groups), number of background antihypertensive medications (3 or >3), and region as factors, and the baseline mean 24hr SBP and mean 24hr DBP as covariates. The intercurrent events and corresponding handling strategy are described in Section 3.2, and the handling of missing not related to intercurrent events in Section 9.3.2 and Section 9.3.4 so that achievement of BP control will be based on imputed mean 24hr SBP and mean 24hr DBP at Week 12. Participants with intercurrent events will be imputed as not having BP control in the analysis.

[figure not shown]
The statistical testing procedure described below will be carried out for the multiple treatment comparisons in the primary and secondary efficacy objectives to ensure that the overall significance level for the multiple hypotheses to be tested is controlled at the one-sided 0.025 level (i.e. two-sided 0.05).

The testing hypotheses associated with secondary efficacy objectives are described below:

- **H**₂₀: No difference in the change of mean 24hr SBP from baseline at Week 12 between highest XXB750 dose versus placebo.
- H₃₀: No difference in average change of mean 24hr SBP from baseline at Week 9 and at Week 12 between highest XXB750 dose versus placebo.

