1.1 Study design

Study XXB750B12201 is a multicenter, randomized, double-blind, placebo-controlled, parallel-group phase 2 study which is comprised of four periods (Figure 1-1):

- A screening period (approximately 7 days)
- A single-blind placebo run-in period lasting approximately 2 weeks
- A 12-week double-blind, placebo-controlled, parallel-group treatment period
- An 8-week safety follow-up period

The study will enroll participants with rHTN defined as participants with uncontrolled BP despite treatment with optimal or maximally tolerated doses of 3 or 4 antihypertensive drugs of different classes, specifically a thiazide/thiazide-like diuretic, an ACEI or an ARB, and a long acting dihydropyridine CCB. The study population will consist of male and female participants 18 years old or older with apparent resistant hypertension as defined in the inclusion and exclusion criteria in the protocol. Approximately 170 participants will be randomized to receive placebo, XXB750 30 mg, 60 mg, 120 mg, or 240 mg SC every 4 weeks, at an overall final ratio of 1:1:1:1:1.

Figure 1-1 Study Design

ABPM = ambulatory blood pressure monitoring; mean 24hr SBP = mean ambulatory systolic blood pressure (based on 24hr ambulatory blood pressure monitoring); msSBP = mean sitting systolic blood pressure (based on office assessment); SC = subcutaneously; WOCBP = women of childbearing potential.

The randomization in this study will be stratified by region (America, Asia except Japan, Japan, Eastern Europe, Western Europe combined with others). The stratification factor will be appropriately accounted for in the planned statistical analysis. At visit 100, all eligible participants will be randomized via Interactive Response Technology (IRT) to one of the allowed treatment arms per design (Figure 1-1).

A staggered approach as summarized in Table 1-1 will divide randomized participants into two groups, which will vary in terms of the ratio of allocation to the treatment arms. Please refer to study protocol Section 4.1 for details.

Table 1-1 Overview of staggered enrollment strategy

Treatment arm	Group 1	Group 2 (adjusted*)	Total (adjusted*)
Placebo	n = 17	n = 17	N = 34
XXB750 30mg SC every 4 weeks	n = 17	n = 17	N = 34
XXB750 60mg SC every 4 weeks	n = 17	n = 17	N = 34
XXB750 120mg SC every 4 weeks	n = 17	n = 17	N = 34
XXB750 120mg SC×1 dose, then XXB750 240mg every 4 weeks	n = 0	n = 34 (0*)	N = 34 (0*)
Group Total	N = 68	N = 102 (68*)	N = 170 (136*)

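### All 240 mg participants enrol in Group 2 but half of placebo enrols in Group 1, and no visible efficacy model adjusts for enrolment group, so drift D biases 240 mg versus placebo by up to about D/2

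*Protocol*

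**What the plan says.** Protocol 4.1 and Table 4-1 (repeated in SAP 1.1, Table 1-1) set out staggered enrolment. Group 1 (about 68) is randomised 1:1:1:1 to placebo, 30, 60 and 120 mg. Group 2 (about 102) is randomised 1:1:1:1:2, with 240 mg added. The groups are consecutive: "Group 2 enrolment will start upon full completion of Group 1 enrollment". Protocol 4.6 places "34 participants on XXB750 dose level 4" in the second group, which is the whole planned arm. If the DMC objects to the top dose, the arm is dropped: "In the event that the DMC recommends that participants should not be exposed to XXB750 240 mg dose, the study will continue without it".

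The SAP recognises that the scheme "will divide randomized participants into two groups, which will vary in terms of the ratio of allocation to the treatment arms". Randomisation is stratified by region only (Protocol 6.3.1, SAP 1.1).

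The primary ANCOVA has "treatment (placebo and XXB750 dose groups), number of antihypertensive medications (3 or >3), and region as factors", with baseline 24-hour SBP as covariate; SAP 2.5.2 matches. The repeated-measures model for H20, the ANCOVA for H30 and the logistic model for H40 (Protocol 9.4.1, SAP 2.6.2) use the same adjustment terms, with visit or baseline DBP where relevant. The imputation, sensitivity and supplementary models (SAP 2.5.3, 2.5.4, 2.5.6, 2.5.7) also have no group or calendar term. Parts of the SAP are redacted, so this covers the visible text.

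Protocol 9.4.1 describes a testing procedure "to ensure that the overall significance level for the multiple hypotheses to be tested is controlled at the one-sided 0.025 level". For the secondary hypotheses, "statistical inference will be made only if the primary hypothesis is rejected" (Protocol 9.3.5).

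**The concern.** A participant's chance of receiving 240 mg is zero in Group 1 and one third in Group 2 (2 of 6 allocation units). Half of the placebo participants compared with 240 mg were therefore randomised when 240 mg was not available. Anything that differs between the two periods and affects the Week 12 change, beyond baseline SBP, drug count and region, is mixed into the 240 mg effect.

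That effect is the whole of H20 and H30, enters H10 through the 240 mg mean, and fixes the top of the fitted curve that informs dose selection. The lower doses share placebo's 17/17 split and are not affected.

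Some drift is plausible. Amendment 1 was issued during enrolment. It lowered the screening office SBP threshold from 145 to 140 mmHg, admitted participants on three or four drugs, and removed the 25% cap on beta-blocker users. The SAP's change table then replaces beta-blocker use by drug count as the covariate. None of this demonstrates drift. How many participants entered under the old criteria is unknown: 39 had been randomised by 23 May 2023, and the amendment still needed ethics approval before it could be implemented.

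**Working it through.** **Inputs.** SD 12 mmHg, 30 evaluable per arm, maximum effect 10 mmHg, one-sided 2.5% (Protocol 9.9.1, 9.9.2). Five candidate models (Protocol 9.3.2). Arm-by-group split from Table 4-1, taken as 15/15 in four arms and 0/30 in 240 mg at 30 per arm. D is assumed to be 1, 2 or 4 mmHg, positive when Group 2 falls more.

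**The plan's own figures first.** SE of 240 mg minus placebo = 12 × √(1/30 + 1/30) = √9.6 = 3.10. Noncentral-t power at 10 mmHg (145 df) is 89.4%; the plan states 89%. With optimal contrasts and a simulated multivariate-t critical value of 2.32, H10 power for Models 1 to 5 is 92.7, 91.9, 95.8, 95.4 and 93.4%. The minimum matches the stated 92%.

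**Bias.** The placebo mean carries D × 17/34 and the 240 mg mean carries D × 34/34. The difference is biased by D × (1 − 0.5) = D/2. For each lower dose the bias is D × (0.5 − 0.5) = 0.

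If the covariate mix also shifts between groups, the model absorbs part of D. With assumed shares on more than three drugs moving from 20% to 40%, the bias is 0.48D; from 10% to 60%, it is 0.39D.

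**Effect on error.** For H20 the noncentrality is (D/2)/3.10. For H10, each contrast shifts by its 240 mg weight times D/2. In Model 4 that weight is 0.760, so at D = 4 the t-statistic shifts by 0.760 × 2 / (12/√30) = 0.69.

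| D (mmHg) | Bias (mmHg) | H10 error | H20 error, taken alone | H20 error behind the H10 gate, global null |
|---|---|---|---|---|
| 0 | 0 | 2.5% | 2.5% | 1.3% |
| 1 | 0.5 | 3.2% | 3.6% | 1.8% |
| 2 | 1.0 | 4.2% | 5.1% | 2.6% |
| 4 | 2.0 | 7.3% | 9.4% | 5.1% |

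H10 error reaches 5% at D = 2.6, or at 2.7 and 3.5 under the two mix shifts. The ungated H20 error is reached only if lower doses work and 240 mg does not. The candidate set does not contain that shape: Models 1 to 4 are monotone, and Model 5 keeps 79% of its peak at 240 mg.

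**Drift the other way.** If Group 2 falls 2 or 4 mmHg less, H20 power drops to 82% or 73%, and minimum H10 power to 88% or 83–84%.

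**With a group factor.** The drift estimate comes from the four arms that span both groups, with variance 144 × (1/60 + 1/60) = 4.8. The adjusted difference subtracts half of that estimate, so its variance is 9.6 + 0.25 × 4.8 = 10.8 and its SE is 3.29, a ratio of √(10.8/9.6) = 1.06. Additive bias becomes zero. H20 power is 85.6%. H10 powers are 91.7, 90.2, 95.3, 92.7 and 93.5%.

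**Mean squared error.** The unadjusted value is 9.6 + (D/2)², against 10.8 adjusted. They are equal at |D| = 2 × √1.2 = 2.19 mmHg.

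**H40.** Drift acts on the logit scale, so D/2 is only approximate, and converting SBP drift into control rates needs assumptions the documents do not supply. No error rate for H40 is relied on here. Minimum power is 76.4% without the factor (stated: 76%) and 76.6% with it.

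**The case against.** The strongest objection is that the harm depends on a number nobody has. D is only what remains in change from baseline after adjusting for baseline SBP, drug count and region, in participants who passed a placebo run-in and an ambulatory threshold of 135 mmHg that Amendment 1 does not list as changed. The sponsor expects no major effect of that amendment on the target population. At D = 1 the bias is 0.5 mmHg against an SE of 3.1. Drug count also captures some of the beta-blocker change. All of this stands, and it limits how large the effect can be said to be.

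Nor is a promise broken. The SAP's statement that "The stratification factor will be appropriately accounted for in the planned statistical analysis" follows directly on region, and region is in the models. The 0.025 statement concerns multiplicity, not time trends. The point is narrower: that error control holds only if residual drift is zero, and neither document states this assumption.

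A third argument is that below about 2.2 mmHg of drift the unadjusted estimate has the smaller mean squared error, so in a phase 2 dose-finding trial a group-adjusted sensitivity analysis would be enough. This is a defensible preference for estimation. It does not protect the formal tests, and it would detect drift poorly: the drift estimate has an SE of √4.8 = 2.2 mmHg, so even D = 4 is under two standard errors.

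**Conclusion.** The concern holds. The imbalance is certain if 240 mg is opened, and does not arise if the DMC rejects it. The bias is up to about D/2 for 240 mg versus placebo in the linear models, and zero for the lower doses, assuming drift is additive and equal across arms. Actual enrolment counts would change the fraction slightly.

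The size of the consequence is uncertain because D is assumed. Over 1 to 4 mmHg, the error of the primary test is 3.2% to 7.3% instead of 2.5%. The gate softens the effect on H20 under the global null, leaving it near nominal at D = 2. The plan should be changed because the correction is cheap and has to be specified before unblinding to be credible. Confidence is high on the structure and moderate on the impact.

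**What to change.** If 240 mg is opened:

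- Add enrolment group (1 versus 2) as a fixed factor in the primary ANCOVA, the H20 repeated-measures model, the H30 ANCOVA and the H40 logistic model. It is estimable because four arms span both groups.
- Derive the MCP-Mod contrasts and critical value from the resulting covariance matrix.
- Add the factor to imputation models only where it can be fitted. It is constant within the 240 mg arm, and retrieved-dropout subsets may be too small.
- Restate power at 30 per arm as about 90% (H10 minimum) and 86% (H20).
- Report 240 mg versus Group 2 placebo as supportive only: 30 against 15 gives an SE of 12 × √(1/30 + 1/15) = 3.79 and power of about 73–74%.
- State two limits. The factor removes additive drift but not a group-by-dose interaction. It is chosen for unbiasedness and error control, since the unadjusted estimate is more precise when drift is small.

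The cost is protocol and SAP wording and one degree of freedom, with no new data. Power falls about 2 points for the H10 minimum, nearly 3 points for H10 under Model 4 (95.4% to 92.7%), and 3 to 4 points for H20. For H40 the minimum is unchanged, but Model 4 falls from 94% to 89%. The 6% rise in SE comes from the arm-by-group layout alone, before the other covariates.
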